**CAIN Protocol Synopsis**

**NCT05432232**

Official Title: The HistoSonics Investigational System for treatment of primary solid renal tumors using histotripsy (CAIN)

NCT Number: NCT05432232

Protocol Date: November 22, 2023 (CSP2276 Revision E)

|  |  |
|--|--|
| Title   | The HistoSonics Investigational System for treatment of primary solid renal tumors using histotripsy (CAIN)  |
| Clinical Investigation Protocol Identification Code | CAIN Sponsor Clinical Study Number: CSP2276 Revision E (22Nov2023)
ClinicalTrials.gov Identifier: NCT05432232   |
| Trial Purpose                                       | The purpose of this trial is to evaluate the technical success and safety profile of the HistoSonics Investigational System for the treatment of primary solid renal tumors.   |
| Trial Design  | This trial is a prospective, multi-center, single-arm pilot trial designed to evaluate the effectiveness and safety profile of the HistoSonics Investigational System in treating primary solid renal tumors. Following histotripsy treatment of the solid renal tumor, subjects will undergo imaging ≤36 hours post-index procedure to determine technical success. Additionally, subjects will be followed 180 days (6 months) post-index procedure, with evaluations at the 14-day, 30-day, 90-day, and 180-day time points to establish the efficacy and safety profile of the HistoSonics Investigational System. |
| Trial Population                                    | Subjects who are 18 years of age or older with a diagnosis of a solid renal tumor.   |
| Objective   | The objective of this trial is to generate data to support a pivotal trial for the HistoSonics Investigational System for use in the kidney.   |
| Device Name   | HistoSonics Investigational System (System)  |
| Indication Under Investigation                      | The indication under investigation is use of the HistoSonics Investigational System for the non-invasive destruction of kidney tissue using histotripsy, a non-thermal mechanical process of focused ultrasound.   |
| Enrollment  | Up to twenty (20) combined male and female subjects treated at up to four (4) clinical sites located in Europe and/or United Kingdom.  |
| Duration of Trial                                   | The duration of this trial is expected to be approximately eighteen (18) months.   |
| Primary Endpoints                                   | 
Primary Effectiveness Endpoint:
 
Technical success defined as complete coverage of the tumor as determined ≤36 hours post-index procedure by magnetic resonance imaging (MRI) or computerized tomography (CT). [Core Lab Adjudicated]
 
Primary Safety Endpoint:
 
Freedom from index procedure related major complications, defined by Clavien-Dindo Classification Grade 3 or higher up to 30 days after the last histotripsy procedure. [Clinical Events Committee Adjudicated]
  |
| Secondary Endpoints                                 | 
 
1. Technique efficacy (primary) defined as the percentage of targeted tumors successfully eradicated post-index procedure assessed via MRI or CT at 90-days post-index procedure without repeat Histotripsy [Core Lab Adjudicated]
 
2. Technique efficacy (secondary) defined as the percentage of targeted tumors successfully eradicated post-index procedure assessed via MRI or CT at 90-days post-index procedure after repeat Histotripsy [Core Lab Adjudicated]
 
   |
| Follow-Up Visits                                    | All treated subjects will have a 14-day, 30-day, 90-day, and 180-day follow up assessment or until the trial is closed, whichever comes first.   |
| General Inclusion                                   | Subjects are eligible for the trial if all the following criteria are met:  |

|                          |  |
|--------------------------|--|
|                          | 
 
1. Subject is <math>\geq 18</math> years of age.
 
2. Subject has signed the Ethics Committee (EC) approved trial Informed Consent Form (ICF) prior to any trial related tests/procedures and is willing to comply with trial procedures and required follow-up assessments.
 
3. Subject is diagnosed with a non-metastatic solid renal mass <math>\leq 3</math>cm confirmed via CT or MRI <math>\leq 30</math> days prior to the index procedure date.
 
4. Subject can tolerate general anesthesia.
 
5. Subject has an Eastern Cooperative Oncology Group Performance Status (ECOG PS) grade 0-2 at baseline screening.
 
6. Subject meets all the following functional criteria at <math>\leq 14</math> days prior to the planned index procedure date:           
 
• White Blood Cell (WBC) <math>\geq 3,000/\text{mm}^3</math>
 
• Absolute Neutrophil Count (ANC) <math>\geq 1,200/\text{mm}^3</math>
 
• Hemoglobin (Hgb) <math>\geq 9 \text{ g/dL}</math>
 
• Platelet count <math>\geq 100,000/\text{mm}^3</math> (<math>\geq 100 \text{ } 10^9/\text{L}</math>)
 
• White Blood Count (WBC) <math>\leq 40 \text{ cells}/\mu\text{L}</math> via urinalysis
 
• Albumin <math>\leq 300,000 \text{ mg/L}</math> via urinalysis
 
 
 
7. Subject has an eGFR <math>\geq 45\text{mL}/\text{min}</math>, <math>\leq 14</math> days prior to the planned index procedure date.
 
8. International Normalized Ratio (INR) score of <math><1.5</math>:           
 
• If on anticoagulants, other than aspirin or non-steroidal anti-inflammatory drugs, assessment must be performed on the day of the procedure; OR
 
• If only on aspirin or non-steroidal anti-inflammatory drugs, assessment must be performed <math>\leq 14</math> days prior to the planned index procedure date; OR
 
• If not on anticoagulants, assessment must be performed <math>\leq 14</math> days prior to the planned index procedure date
 
 
 
9. Biopsy is required to determine the type of tumor and must be performed <math>\geq 14</math> days prior to the planned index procedure date.
 
 |
| Imaging Inclusion | 
 
10. The tumor selected for histotripsy treatment must be <math>\leq 3</math>cm in longest diameter.
 
11. Subject has an adequate acoustic window to visualize targeted tumor using the HistoSonics Investigational System.
 
12. Subject will undergo histotripsy treatment of only one (1) tumor during the index procedure, regardless of how many tumors the subject has.
 
  |
| General Exclusion | 
Subjects are not eligible for participation in the trial if any of the following criteria are met:
 
 
1. Subject is pregnant or planning to become pregnant or nursing (lactating) during the trial period.
 
2. Subject is enrolled and being actively treated in another investigational pharmaceutical or device trial <math>\leq 30</math> days prior to planned index procedure date.
 
   |

|  |   |
|--|---|
|  | 

3. Subject is undergoing active chemotherapy for any cancer ≤14 days prior to planned index procedure date.

4. Subject is undergoing active immunotherapy ≤40 days prior to planned index procedure date.

5. In the Investigator's opinion, the subject has co-morbid disease(s) or condition(s) that would cause undue risk and preclude safe use of the HistoSonics Investigational System.

6. Subject is on dialysis or being considered for dialysis.

7. Subject has not recovered to Common Terminology Criteria for Adverse Events (CTCAE) grade 2 or better from any adverse effects (except alopecia and neuropathy) related to previous anti-cancer therapy.

8. Subject has an uncorrectable coagulopathy other than that induced by aspirin or non-steroidal anti-inflammatory drugs.

9. Subject has a planned cancer treatment (e.g., nephrectomy, chemotherapy, immunotherapy etc.) prior to completion of the 30-day follow-up visit.

10. Subject has had previous treatments with chemotherapy, radiotherapy, or both that have not been discontinued ≥14 days prior to the planned index procedure date and have not recovered (CTCAE grade 2 or better) from related toxicity (exclusive of alopecia and neuropathy).

11. Subject has previous treatment with immunotherapies that has not been discontinued ≥40-days prior to the planned index procedure date and has not recovered from related toxicity (CTCAE grade 2 or better).

12. Subject has a life expectancy less than one (< 1) year.

13. In the investigator's opinion, histotripsy is not a treatment option for the subject.

14. Subject has a concurrent condition that could jeopardize the safety of the subject or compliance with the protocol.

15. Subjects' targeted tumor has had prior locoregional therapy (e.g., ablation, embolization, radiation).

16. Subjects' tumor is not treatable by the HistoSonics Investigational System's working ranges (refer to User Guide).

17. In the physician's opinion, the anticipated risk of intervention outweighs the potential benefits of the intervention.

18. Subject has acute renal failure.

19. Subject has a genetic predisposition to kidney cancer such as:

• Von Hippel Lindau (VHL)

• Hereditary Papillary Renal Carcinoma (HPRC)

• Birt-Hogg-Dubé Syndrome (BHD)

• Tuberous Sclerosis Complex (TSC)

• Hereditary Leiomyomata's Renal Cell Carcinoma (HLRCC)

• Reed's Syndrome

 |
|--|---|

|                            |  |
|----------------------------|--|
|                            | 

• Succinate Dehydrogenase B Deficiency (SDHB)

• BRCA 1 associated protein -1 (BAP1) Renal Cell Carcinoma

• MITF predisposed Renal Cell Carcinoma

 
20. Tumor is an angiomyolipoma.
 
21. Subject has a known sensitivity to contrast media and cannot be adequately pre-medicated.
   |
| Imaging Exclusion   | 
22. The targeted tumor is not clearly visible with diagnostic ultrasound and either magnetic resonance imaging (MRI) or computerized tomography (CT).
 
23. Targeted tumor with adequate margin overlaps the renal pelvis, main renal vessel, ureter, or other vital structure.
 
24. Targeted tumor with adequate margin overlaps a non-targeted tumor visible via imaging.
 
25. The treatment of the tumor will not allow for an adequate margin as determined by the investigator.
 |
| Statistical Methods | All endpoints will be summarized descriptively with 95% (Wilson) confidence intervals. As a pilot trial, no formal hypotheses will be defined; the endpoints are designed to provide additional information for the development of a pivotal trial.  |
| Sponsor             | HistoSonics, Inc.
[name]
[name]
United States of America (USA)
[contact]   |

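### The primary safety endpoint counts complications of the index procedure only, but its window runs from the last histotripsy, so read literally a major complication of a repeat treatment is not a failure

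*Combined protocol and SAP*

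**What the plan says.** Under Primary Endpoints, the synopsis defines the safety endpoint as "Freedom from index procedure related major complications, defined by Clavien-Dindo Classification Grade 3 or higher up to 30 days after the last histotripsy procedure", adjudicated by the Clinical Events Committee. No other safety endpoint is listed.

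Under Secondary Endpoints, technique efficacy comes in two forms. Item 1 is "assessed via MRI or CT at 90-days post-index procedure without repeat Histotripsy"; item 2 is "assessed via MRI or CT at 90-days post-index procedure after repeat Histotripsy". Repeat treatment is therefore foreseen, and both items take the index procedure as their time origin.

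The index procedure is used as a single dated event elsewhere too. Under Trial Design, the technical-success imaging (within 36 hours) is timed from it, and "subjects will be followed 180 days (6 months) post-index procedure". Imaging Inclusion item 12 reads "Subject will undergo histotripsy treatment of only one (1) tumor during the index procedure".

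Enrollment is "Up to twenty (20) combined male and female subjects treated". Under Statistical Methods, "All endpoints will be summarized descriptively with 95% (Wilson) confidence intervals"; no hypotheses are defined, and "the endpoints are designed to provide additional information for the development of a pivotal trial".

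**The concern.** The two halves of the safety definition point at different procedures. One half says which complications count (those related to the index procedure). The other says how long to look (30 days past the last histotripsy). For a subject treated once, index and last are the same procedure and nothing is lost. For a retreated subject they differ, and a complication caused by the repeat falls inside the window but outside the attribution.

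The discrepancy has one direction. Compared with a definition that counts every histotripsy procedure, the literal one can only give an equal or higher freedom rate. Secondary endpoint 2, meanwhile, credits tumor eradication achieved after a repeat. On the literal reading the benefit of a repeat is counted and its major complications are not. The reported rate and interval are what the pilot hands to the pivotal trial's planners, and they would depend on which reading the committee happens to adopt.

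**Working it through.** **Step 1. Does the index procedure include repeats in this document?**

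- Secondary endpoints 1 and 2 have the same time origin (90 days after the index procedure) and differ only in whether a repeat took place. If repeats were part of the index procedure, the split would have no meaning.
- The 36-hour imaging and the 180-day follow-up both need one fixed date.
- Inclusion item 12 fits this usage but is weak support, since it limits the number of tumors rather than sessions.
- No part of the synopsis gives a broader definition.

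So the text keeps the two apart, and the literal reading leaves repeat-related complications uncounted.

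**Step 2. What one subject is worth at n = 20.** The plan states no target rate or interval, so there is no figure of its own to reproduce. One subject is 1/20 = 5 points. The 95% Wilson limits, with z = 1.96 and p = x/n, are

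[p + z²/(2n) ± z·√(p(1−p)/n + z²/(4n²))] / (1 + z²/n)

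| Free of failure | Rate | 95% Wilson interval | Fall in lower limit from the row above |
|---|---|---|---|
| 20/20 | 100% | 83.9–100.0% | – |
| 19/20 | 95% | 76.4–99.1% | 7.5 points |
| 18/20 | 90% | 69.9–97.2% | 6.5 points |
| 17/20 | 85% | 64.0–94.8% | 5.9 points |

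The 7.5-point fall applies only if there is no other failure.

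**Step 3. How likely a difference is.** The documents give neither a retreatment rate nor a complication rate, so both are assumed here: 20 index procedures, each with major-complication risk q; r subjects retreated once at the same q; all independent. A retreated subject is classified differently only if the repeat causes a major complication and the index procedure did not, so p = q(1−q). Then:

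- expected shift in the rate = r·p/20
- chance that at least one subject is classified differently = 1 − (1−p)^r
- expected fall in the Wilson lower limit, by enumerating all combinations of index-related and repeat-related failures
- chance that there is no index-related failure and at least one repeat-related one, so that the literal reading gives 20/20 and the inclusive reading does not

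Example, q = 0.05 and r = 4: p = 0.05 × 0.95 = 0.0475; shift = 4 × 0.0475/20 = 0.0095, or 0.95 points; chance of any = 1 − 0.9525⁴ = 17.7%.

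| q | r | Expected shift (points) | Chance of any difference | Expected fall in lower limit (points) | Chance of a drop from 20/20 |
|---|---|---|---|---|---|
| 2% | 2 | 0.20 | 3.9% | 0.28 | 2.6% |
| 2% | 4 | 0.39 | 7.6% | 0.56 | 5.2% |
| 2% | 8 | 0.78 | 14.6% | 1.11 | 10.0% |
| 5% | 2 | 0.47 | 9.3% | 0.64 | 3.5% |
| 5% | 4 | 0.95 | 17.7% | 1.27 | 6.6% |
| 5% | 8 | 1.90 | 32.2% | 2.51 | 12.1% |
| 10% | 2 | 0.90 | 17.2% | 1.10 | 2.3% |
| 10% | 4 | 1.80 | 31.4% | 2.19 | 4.2% |
| 10% | 8 | 3.60 | 53.0% | 4.32 | 6.9% |

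These ranges have no floor above zero. With nobody retreated the effect is nil. With one subject retreated, the shift is 0.10 to 0.45 points and the chance of any difference 2% to 9%.

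**Step 4. Does follow-up cover the inclusive reading?** A repeat credited by secondary endpoint 2 happens no later than the 90-day imaging. Its window ends by about day 90 + 30 = 120, inside the 180 days.

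**The case against.** The strongest reply is that the window itself shows the intent: tying it to the last histotripsy is hard to explain unless repeats were meant to count, and the committee may already work that way. This is fair, and it probably identifies the attribution phrase as the slip. It does not settle the matter, because the attribution phrase is what tells the committee which events count.

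Second, only a synopsis is available. A full protocol or committee charter may define the term. This also stands, and it limits the finding to the synopsis as written. The point is nonetheless a conflict between two phrases that are present, not a complaint about missing detail.

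Third, the analysis is descriptive, at most 20 subjects are treated, and nothing suggests that a serious event after a repeat would go unrecorded, since safety is followed to 180 days. All true. No test, error rate or decision rule is affected; what is affected is how an event is classified in one reported rate. Because that rate is the only listed safety endpoint, the effect still matters.

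Fourth, the size depends on assumed retreatment and risk figures. It does, and other plausible assumptions would widen the range. The direction does not depend on them.

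Fifth, the synopsis sets no latest date for a repeat, and one after day 150 would have a window running beyond day 180. That is so under the window as already written; changing the attribution does not create it.

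**Conclusion.** The concern holds for the synopsis as written. Attribution and window refer to different procedures, and the literal rule leaves a Grade 3 or higher complication of a repeat histotripsy outside the primary safety rate. This is an inconsistency to align, not evidence that the sponsor means to exclude repeats.

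The size is modest and conditional: 5 points on the rate per affected subject at n = 20, and an expected shift of 0.2 to 3.6 points across the assumed scenarios with 2 to 8 subjects retreated. The largest single step, out of 20/20, has only a 2% to 12% chance in those scenarios. It should be fixed, and before any event is adjudicated, so that the reading is not chosen once outcomes are known. Confidence is medium, because the full protocol and committee instructions have not been seen.

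**What to change.** In the primary safety endpoint, replace the attribution to the index procedure with attribution to any histotripsy procedure (index or repeat). Count it per subject up to the existing limit of 30 days after the last histotripsy, and use the same wording in the Clinical Events Committee instructions. If the full protocol already defines the index procedure to include repeats, state that definition in the synopsis instead, and check that the two secondary endpoints still make sense under it. Optionally, add a supportive row for index-related events within 30 days of the index procedure, so that the safety of a single treatment can also be read off.

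The cost is one phrase in two documents and possibly a slightly less favourable rate. The sample size does not change, and the window stays as it is, so the change adds no follow-up. For a repeat by the 90-day imaging, the existing follow-up covers the window unless the trial closes early.

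### Does reading technique efficacy after repeat histotripsy at day 90 from index, whenever the repeat took place, call for a change to the plan?

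*Combined protocol and SAP*

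**What the plan says.** Under Secondary Endpoints, the synopsis defines technique efficacy twice. Item 1 is read "at 90-days post-index procedure without repeat Histotripsy". Item 2 counts targeted tumours "successfully eradicated post-index procedure assessed via MRI or CT at 90-days post-index procedure after repeat Histotripsy". Both are core-lab reads, and both are timed from the index procedure.

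The Trial Design row also counts follow-up from index, "with evaluations at the 14-day, 30-day, 90-day, and 180-day time points to establish the efficacy and safety profile" of the system. The Follow-Up Visits row ends with a "180-day follow up assessment or until the trial is closed, whichever comes first". No visit is tied to a repeat procedure. The synopsis gives no window for repeats, no minimum time from repeat to scan, and no denominator for item 2 beyond targeted tumours.

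The Primary Safety Endpoint has a window that does move with a repeat: "up to 30 days after the last histotripsy procedure".

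Imaging Inclusion item 12 fixes the unit of analysis: "Subject will undergo histotripsy treatment of only one (1) tumor during the index procedure". Statistical Methods calls for descriptive summaries with 95% Wilson intervals and no formal hypotheses, and adds that "the endpoints are designed to provide additional information for the development of a pivotal trial".

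**The concern.** A tumour treated once is seen 90 days after its treatment. A tumour treated again is seen sooner after its last treatment, by as many days as the repeat followed index. Item 2 can therefore put into one percentage tumours observed for quite different periods, and the percentage does not show which is which. A repeat given after the day-90 scan would appear in neither efficacy endpoint.

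The safety endpoint sharpens the impression. Its window extends after a repeat while the efficacy read stays put, so for a repeat after day 60 (60 + 30 = 90) the safety window closes later than the efficacy scan.

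The trial exists to inform a pivotal trial. If the pivotal planners took item 2 as eradication about three months after final treatment, they could misjudge it, in a direction that the documents do not allow one to predict.

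**Working it through.** The plan gives no power or sample-size calculation, so there is no figure of its own to reproduce. The check asks what the timing does to the reported result.

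**Inputs from the synopsis.** Read at day 90 from index (Secondary Endpoints, items 1 and 2). At most 20 subjects (Enrollment) with one tumour each at index (Imaging Inclusion item 12), so at most 20 tumours. Wilson 95% intervals (Statistical Methods).

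**Assumed, because the synopsis does not state them.** The repeat day t, the number retreated r, and 15 of 20 tumours eradicated without repeat.

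**1. Interval from repeat to scan** = 90 - t, taking the scan on its nominal day.

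| Repeat day t | Days to the day-90 scan | Day from index if read 90 days after the repeat (t + 90) |
|---|---|---|
| 2 | 88 | 92 |
| 30 | 60 | 120 |
| 60 | 30 | 150 |
| 85 | 5 | 175 |

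The text therefore permits intervals from near 0 to just under 90 days. It does not show that they occur: with no repeats, or with all repeats on one day, there is no variation among retreated tumours.

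**2. Weight of retreated tumours**, if the denominator is all 20: r/20, which is 5% for r = 1, 10% for r = 2 and 20% for r = 4.

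**3. Effect on the endpoint.** The Wilson limits are [p + z²/2n ± z√(p(1 - p)/n + z²/4n²)] / (1 + z²/n), with z = 1.96. For 15/20, z² = 3.84, the centre is (0.75 + 0.096)/1.192 = 0.710 and the half-width is 1.96 × 0.1085/1.192 = 0.178, giving 53.1% to 88.8%.

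- Item 1: 15/20 = 75% (53.1 to 88.8).
- Item 2, if all r retreated tumours are read as eradicated: r = 1, 16/20 = 80% (58.4 to 91.9); r = 3, 18/20 = 90% (69.9 to 97.2); r = 5, 20/20 = 100% (83.9 to 100).
- Item 2 minus item 1 = r/20 in each case: 5, 15 and 25 points.

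The repeat day t appears nowhere in these formulas. Knowing it helps interpretation but leaves every estimate and limit as it was. With a common denominator, the difference between the items is already the share of tumours that were retreated and then read as eradicated at day 90.

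**4. Would a separate rate for retreated tumours help?** No. At the likely counts it is nearly empty: 2/2 gives 34.2% to 100%, and 3/4 gives 30.1% to 95.4%.

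**5. Would restarting the clock at the repeat help?** It would equalise the intervals, but the last column of the table shows reads on days that are not scheduled visits. Item 2 would also no longer be measured on the same day as item 1, so their difference would lose its plain meaning.

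**6. The denominator.** The synopsis does not say whether item 2 covers all targeted tumours or only retreated ones. Both items take targeted tumours as their base, so all targeted tumours is the natural reading. On a retreated-only reading the intervals could still vary, and the day-90 status would still be well defined.

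**The case for a change.** The best case for a change is that the sponsor plainly foresaw repeats, wrote a moving clock for safety, and wants the results for pivotal planning. One clear label on item 2, with a tumour-by-tumour listing of repeat day, interval to scan and core-lab status, would cost almost nothing and would be better fixed before results are known.

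Part of this stands. On the synopsis text the interval can vary, item 2's denominator is not spelled out, and such a listing would be useful.

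The rest is weaker. The safety contrast proves little: the same sentence confines the endpoint to major complications attributed to the index procedure, so it is not clear that complications of the repeat count at all. Complications and eradication may in any case reasonably run on different clocks. A label saying that only repeats before the scan count restates what the definition already implies. Repeats after the day-90 scan are hypothetical, since the synopsis never says that they are allowed. Using day 180 to follow retreated tumours would presume imaging at that visit, which the synopsis does not mention. Finally, the public text is a synopsis: the timing of repeats, scan windows and data listings normally belong in the full protocol, and their absence here does not show that they are absent there.

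**Conclusion.** No change to the plan is needed. Item 2 is a fixed-day landmark: the state of the tumour 90 days after the strategy began, allowing for retreatment. That is a legitimate quantity, and the shared day makes it comparable with item 1. Following the plan as written gives a sound descriptive result with no error rate, power or decision rule at risk.

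The size is modest: up to 5 points per retreated tumour if all 20 tumours are in the denominator, with intervals of 88 to 5 days for assumed repeats between days 2 and 85. Neither the repeat days nor the number retreated can be learned from the synopsis, and the direction of any bias is unknown.

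What remains is missing detail of the kind that analysts supply in reporting: naming the denominator and showing, for the few retreated tumours, when the repeat took place and how long before the scan. This conclusion assumes that the dates of treatment and imaging are recorded for each subject, and that item 2 is presented as what it is, status at day 90 from index, and not as eradication three months after the final treatment.

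### Inclusion 6 caps urinary albumin at 300,000 mg/L (300 g/L), a level no urine sample could plausibly exceed, so the criterion excludes nobody as printed

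*Combined protocol and SAP*

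**What the plan says.** The document available is the synopsis of protocol CSP2276 Revision E. General Inclusion item 6 opens with "Subject meets all the following functional criteria at" and gives a window of 14 days before the planned index procedure. Six bullets follow: blood white cells, neutrophils, haemoglobin, platelets, and two urinalysis measures. The last is "Albumin \leq 300,000 \text{ mg/L} via urinalysis".

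The platelet bullet is the only one printed in two units: "Platelet count \geq 100,000/\text{mm}^3 ( \geq 100 \text{ } 10^9/\text{L".

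Renal status and risk are also screened elsewhere:

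- General Inclusion item 7: "Subject has an eGFR \geq 45\text{mL}/\text{min".
- General Exclusion item 6: "Subject is on dialysis or being considered for dialysis".
- General Exclusion item 18: "Subject has acute renal failure".
- General Exclusion items 5, 14 and 17 rest on comorbidity, concurrent conditions and judgement. Item 17, for example, applies where "the anticipated risk of intervention outweighs the potential benefits of the intervention".

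No other part of the synopsis gives a urinary albumin limit.

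**The concern.** An upper limit works as an eligibility criterion only if some candidates could exceed it. A limit of 300 g/L of albumin in urine is several times the concentration of albumin in blood, so every candidate would pass. The sponsor chose to make urinary albumin a separate mandatory requirement alongside eGFR, in a trial of a device intended to destroy kidney tissue. As printed, that requirement does nothing. A candidate with heavy albuminuria would be stopped only if another renal criterion or an investigator's judgement happened to catch the case.

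What is at stake is the make-up of the treated population. The stated objective is to generate data to support a pivotal trial, so an uncorrected figure could also be carried into that trial's criteria.

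**Working it through.** **Inputs from the synopsis (General Inclusion item 6)**

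- Urinary albumin limit: 300,000 mg/L.
- Platelet floor: 100,000/mm³, also printed as 100 × 10⁹/L.
- Haemoglobin floor: 9 g/dL = 90 g/L.
- White-cell floor 3,000/mm³ and neutrophil floor 1,200/mm³.

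**Inputs assumed (not in the documents)**

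- Blood albumin: 30 to 60 g/L, with 100 g/L as a deliberately extreme check.
- Urine albumin in heavy albuminuria: 1.75 to 80 g/L.

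**Step 1: convert the limit.** 300,000 mg/L ÷ 1,000 = 300 g/L. Then 300 g/L ÷ 10 = 30 g/dL = 30% w/v.

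**Step 2: check how the comma is used.** With a thousands separator, 100,000/mm³ × 10⁶ mm³/L = 1.0 × 10¹¹/L = 100 × 10⁹/L, which reproduces the second printed value. With a decimal comma, 100/mm³ = 0.1 × 10⁹/L, a factor of 1,000 away from it. The white-cell and neutrophil floors would likewise fall to 3 and 1.2 cells per mm³. The list is coherent only with a thousands separator, so the albumin limit is three hundred thousand mg/L.

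**Step 3: compare the limit with plausible concentrations.**

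| Comparator | Value (g/L) | 300 ÷ value |
|---|---|---|
| Blood albumin, low (assumed) | 30 | 10 |
| Blood albumin, high (assumed) | 60 | 5 |
| Blood albumin, extreme check (assumed) | 100 | 3 |
| Urine albumin, low end of heavy albuminuria (assumed) | 1.75 | 171 |
| Urine albumin, high end of heavy albuminuria (assumed) | 80 | 3.75 |
| Haemoglobin floor in the same list (scale only) | 90 | 3.3 |

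The row that decides the matter is urine at 80 g/L, the value most favourable to the printed limit. The limit is not reached even there.

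**Step 4: look for a substitute.** Inclusion 7 concerns eGFR, exclusion 6 dialysis and exclusion 18 acute renal failure. Exclusions 5, 14 and 17 are general conditions or judgements. They may remove some of the same candidates, but none states an albumin concentration, so none does the work of this bullet.

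**The case against.** The strongest objection is that the error may lie in the reading of the PDF and not in the plan. The point turns on one unit, and a lost micro sign would change the limit by a factor of 1,000 and remove the defect. The line gives no second unit, and the limit is not repeated elsewhere. This possibility stands, but it is unlikely: the number and unit are cleanly rendered, and the micro sign survives in the bullet directly above. The sponsor can settle it by looking at its own source.

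A related objection is that sites are in Europe and/or the United Kingdom, so the figure might come from a laboratory that uses decimal commas. The thousands-separator reading is an inference, though the platelet, white-cell and neutrophil lines all support it. If a site did read the comma as a decimal, it would apply a limit 1,000 times different from the printed one, and the line would still need correcting.

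Three further points limit what can be claimed:

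- Only the synopsis is visible. Whether the full protocol carries the same figure, or whether sites worked from it, is unknown.
- The practical effect is bounded. The other renal and risk criteria remain in force, and the trial is a descriptive pilot without formal hypotheses.
- Subjects already treated satisfied the criterion then in force. A later check of their values cannot turn them into screen failures, and the synopsis does not say whether albumin was recorded as a number. That narrows the purpose of the check but does not make it pointless.

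**Conclusion.** The concern holds as stated. The printed limit excludes nobody, so either the number or the unit is wrong. It is 5 to 10 times an assumed blood albumin of 30 to 60 g/L, and at least 3.75 times an assumed urinary albumin of up to 80 g/L. The conversion is exact. Only the comparators are assumptions, and no value in the ranges shown reverses the conclusion.

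The effect is on eligibility and on the composition of a group of up to 20 treated subjects. No effect on the endpoint definitions, the Wilson intervals or the safety estimate is claimed. The number of subjects affected cannot be given, because the synopsis states neither the number screened nor the intended limit. This should be fixed; it does not undermine the analysis.

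**What to change.** 1. Check the albumin figure and its unit against the sponsor's laboratory source and the full protocol.
2. Correct item 6 wherever it appears. Printing the limit in two units, as the platelet bullet does, would make a future slip visible.
3. Where numeric screening urinalysis results are on file, compare them with the corrected limit and report how many treated subjects lie above it, as a description of the population.

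The sponsor must supply the intended limit; none is proposed here.

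The cost is one corrected figure or unit in the next amendment and one check of existing data. The downside is possible additional screen failures among subjects still to be enrolled. Their number depends on the corrected limit and cannot be estimated from the documents.
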